**Bacterial Decolonization to Prevent Radiation Dermatitis: A Randomized
Controlled Trial and Quality of Life Assessment**

NCT #03883828

Study Protocol

Document Date 5/13/19

Table of Contents

1. Description of the study	3
2. Background	3-4
3. Objectives	4
4. Study Design	4
4.1 Subject inclusion criteria.....	4
4.2 Patient exclusion criteria	4
4.3 Recruitment.....	4
4.4 Study procedures	5
4.5 Study calendar and timeline	6-7
4.6 Consent	7
5. Statistical analysis and sample size calculation:	7-8
6. Data monitoring and safety	8
6.1 Data storage	8
6.2 Confidentiality	8
6.3 Source documents	9
6.4 Adverse reporting and monitoring.....	9-10
7. Appendix	10
8. References	16

1. Description of the study:

The purpose of this study is to determine whether bacterial decolonization of the nares and skin prior to treatment with radiotherapy (RT) for patients with cancers of the head and neck or breast, can prevent high-grade radiation dermatitis (RD) and improve quality of life. This study is being conducted because prior studies from this research group have found bacterial colonization in the nose prior to initiation of RT to be associated with an increased risk of high grade RD. Patients in the treatment arm will receive pretreatment with mupirocin ointment to the nares and chlorhexidine gluconate wash to the body, while patients in the control arm will receive standard of care treatment. Bacterial cultures will be taken from the nares, radiated skin, and site contralateral to radiation at baseline and at completion of RT from all participants. If severe infection requiring systemic antibiotics occurs, we may obtain additional cultures. Participants will also participate in a quality of life questionnaire before and after RT.

2. Background:

RD is a common and often debilitating adverse event associated with the use of fractionated external beam RT for the treatment of numerous cancers. RD may occur within hours to weeks of exposure to radiation and often worsens throughout the course of treatment.¹ Symptoms include itching and pain which can severely affect quality of life.² RD occurs in up to 95% of patients who receive RT for curative cancer treatment and rates are highest amongst patients treated for breast, head and neck, and anogenital cancers.³ The most commonly used grading instrument for RD, the Common Terminology Criteria for Adverse Events (the CTCAE), grades RD on a scale of 0-5, with higher grades indicating more severe involvement as seen in figure 1.⁴

Direct damage to keratinocytes in addition to local inflammation are proposed to cause RD, however the pathogenesis of the subsequent inflammation is not well understood. One proposition is that bacteria on the skin may increase the risk of severe RD by increasing inflammation and preventing the natural re-epithelialization of the keratinocytes exposed to radiation.⁵ Several case reports have shown that secondary infection with bacteria such as *Staphylococcus Aureus* (SA) has been implicated in RD, and they propose that bacteria exacerbates dermatitis via activation of MHC class II molecules on immune cells.¹ The association between SA infection and RD was also confirmed in a small study which found that 23% of RD patients had secondary skin infections and that a large subset of those patients (57%) developed grade 4 RD.⁶

In a recent study, our group discovered that nasal colonization with any bacteria and specifically with SA prior to RT was a powerful predictor of high-grade RD. Further supporting the role of bacteria in the pathogenesis of RD, we found more SA on the radiated skin after treatment in patients with high grade RD. These findings were consistent with similar results in other inflammatory skin diseases such as atopic dermatitis and mycosis fungoides, where SA has been shown to play an important role in skin inflammation.^{7,8} Prior studies have not looked at bacterial decolonization as a strategy to prevent RD. The goal of this study is to assess the efficacy of bacterial decolonization in patients prior to and during RT. The study outcomes have the potential to change the way we approach prevention of RD in cancer patients.

Universal bacterial decolonization using similar strategies to what we are proposing have been shown to be safe and cost effective in other disease states, and is

now the standard of care in the intensive care unit and prior to orthopedic surgery in order to prevent infectious complications. For example, Huang et al found that universal SA decolonization with chlorhexidine and mupirocin dramatically decreased methicillin resistant staphylococcus aureus (MRSA) prevalence and MRSA-associated hospitalizations in a county-wide study.⁹ A recent systematic review of 19 studies showed that there was a reduction in surgical site infections and wound complications after institution of a SA screening and decolonization protocol.¹⁰

This study will focus on preventing RD in patients with breast and head/neck cancer, as these cancer types are associated with the highest incidence of RD. Anogenital cancers will not be included in this study, as too few patients from this category were recruited in our preliminary study to achieve statistical significance. Furthermore, this study excludes patients receiving RT for palliative intent as these patients receive few treatments and are unlikely to develop radiation dermatitis. By implementing a similar decolonization protocol in patients receiving RT, we hope to prevent the development of RD and improve quality of life.

3. Objectives and endpoints:

1. The primary goal is to determine if bacterial decolonization prior to RT prevents development of high grade RD (grade 2-5). The primary endpoint is the incidence of high grade RD at the end of the trial.
2. The secondary goal is to assess if the intervention improves quality of life compared to the control arm. The secondary endpoint is the quality of life, assessed by the Skindex-16.

4. Study Design:

4.1 Subject inclusion criteria:

1. Age ≥ 18
2. Diagnosis of a solid tumor of the breast or head and neck with plans for fractionated RT (≥ 15 fractions) with curative intent, including post-operative patients deemed eligible for RT by their surgeons and radiation oncologists

4.2 Patient exclusion criteria:

1. Prior RT to the region of interest
2. Existing dermatologic condition affecting the treatment area (eg: atopic dermatitis, psoriasis, and non-healing wounds)
3. Known allergy to chlorhexidine or mupirocin

4.3 Recruitment:

Patients will be recruited from the Montefiore-Einstein Department of Radiation Oncology. Study physicians will identify patients seen in their clinics that meet the study's inclusion criteria. We aim to recruit up to 80 patients for the study. Adult patients with breast or head and neck cancer receiving curative radiation therapy will be eligible for the study. There will be no compensation for the study.

4.4 Study Procedures

This trial will be a randomized controlled trial assessing the efficacy of universal bacterial decolonization in preventing high-grade RD. Therefore, all participants, regardless of baseline culture results, will be 1:1 randomized to one of two arms: the intervention arm and the control arm. The randomization will be performed in a stratified manner within each of the two cancer types (breast cancer or head and neck cancer).

All patients, regardless of treatment arm, will receive a complete history and physical exam during their screening visit. Patients in the control arm will be treated according to standard of care without any RD prophylaxis. Patients in the intervention arm will receive a decolonization regimen, which is accepted as standard of care and commonly used in other patient populations (ICU and prior to orthopedic surgery). The decolonization regimen will consist of intranasal mupirocin ointment to be applied twice daily to the nares and chlorhexidine wash to be used once daily to the body. This combined regimen will be conducted by the patient for 5 consecutive days prior to the start of RT, and will be repeated for an additional five days every 2 weeks for the duration of RT, according to standard of care decolonization methods.⁹ Should a patient experience an adverse reaction to the topical chlorhexidine gluconate solution or mupirocin ointment, the principal investigator may discontinue their participation from the study and, depending on severity of adverse effect, remove the offending agent and treat any resulting rash or skin discomfort. This will not affect their radiation therapy treatment, and they will continue to receive standard of care radiation therapy.

Chlorhexidine and mupirocin will be prescribed by the principal investigator prior to the start of radiation therapy, at no cost to the patient. Patients will be supplied with a calendar showing the dates of decolonization and asked to document their decolonization regimen to monitor for compliance. Standardized photographs of the radiated area will be taken at baseline, and at the end of RT for purposes of grading. Should a patient refuse photographs, they may still participate in the study. Grading scores from the treating radiation oncologist's note in the electronic health record will be used in place of clinical photographs. Research funds from the division of dermatology and radiation oncology will be used to pay for bacterial culture swabs, wound culture laboratory fees, mupirocin, and chlorhexidine solutions. Should a patient in any treatment arm develop symptomatic RD or RD that is grade 2 or higher, the patient will be treated by the radiation oncologist. There is no restriction on use of topical or oral antibiotics as needed during the study. Patients may be treated by the radiation oncologist with other topical preparations including Aquaphor and/or silver sulfadiazine regardless of treatment arm.

The SKINDEX-16 questionnaire will be used prior to initiation of RT and at completion of RT to assess whether decolonization can improve patient quality of life. Validated in 2001, this questionnaire assesses domains of symptoms, emotions, and functioning. This questionnaire is commonly used in the evaluation of dermatologic diseases including RD, as it has demonstrated both content and construct validity in previous studies.¹¹ For example, one recent clinical trial that assessed mometasone furoate for the prevention of RD in breast cancer patients also utilized the SKINDEX-16 to assess quality of life as a secondary measure.¹² Furthermore, our preliminary study showed that patients with more severe RD were impacted more severely than patients without RD in all three domains (data submitted for publication).

Finally, de-identified samples from superficial skin swabs will be placed in a storage buffer meant to preserve bacterial nucleotides and kept in a freezer at -80C for

future microbiome analysis. Bacterial RNA and DNA will then be extracted from the samples in order to perform skin microbiome analysis via whole-community metagenomics sequencing and RNA transcriptomics sequencing. Of note, only bacterial samples from culture swabs will be stored for future microbiome analysis of the skin flora. No DNA from participants will be stored.

Study evaluations will include:

Before RT and within two weeks of completion of RT:

- Bacterial cultures obtained via a superficial swab from (1) the nares, (2) skin at the irradiated site and (3) contralateral or other non-radiated skin. This is a non-invasive test using a cotton-tipped applicator inserted into the nostrils or rubbed on the skin.
- Superficial swabs from the same 3 sites will be obtained in the same manner to be stored in a -80° C freezer for future de-identified microbiome analyses.
- Standardized photographs of skin at radiated site to be graded by a dermatologist blinded to study arm. Additional photographs or notes from the chart may be taken in the case of that severe RD develops during treatment.
- Quality of Life assessment using the Skindex-16 questionnaire.¹⁰

Before and during RT:

- Patients will be asked to initial each date on the supplied calendar when they complete the decolonization protocol in order to assess compliance.

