4.6 Consent

Consent will be performed in the Montefiore-Einstein Center for Cancer Care Radiation Oncology clinics. The study PI, co-investigators, and key personnel will all participate in providing the informed consent to possible study participants. Study key personnel, which includes the treating radiation oncologists, will identify eligible patients. These personnel will then explain the study, explain the consent form, ask the patient if they have any questions, and confirm that they are willing to participate in the study.

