6.4 Adverse Event Monitoring and Reporting

As this is an interventional protocol, any adverse events will be recorded and reported. Both mupirocin and chlorhexidine are topical medications that are routinely used in the hospital setting, therefore few adverse events are expected. Because this is small single site study with no more than minimal risk expected, the study principle investigator (PI) will monitor closely for adverse events. The treating radiation oncologist will assess for adverse events at each radiotherapy visit as well. Any unanticipated or serious events (grade 3 or higher) related to participation in this study will be investigated by the study PI and reported to the Einstein IRB. All adverse events will be recorded in an electronic document that is de-identified. This adverse events log, attached in the appendix, will then be submitted to the IRB at the time of protocol renewal.

Unanticipated problems, defined by the Office for Human Research Protections (OHRP) include any incident, experience, or outcome that meets all of the following criteria:

1. Unexpected (in terms of nature, severity, or frequency) given (a) the research procedures that are described in the protocol-related documents, such as the IRB-approved research protocol and informed consent document; and (b) the characteristics of the subject population being studied;

2. Related or possibly related to participation in the research (in this guidance document, possibly related means there is a reasonable possibility that the incident, experience, or outcome may have been caused by the procedures involved in the research); and
3. Suggests that the research places subjects or others at a greater risk of harm (including physical, psychological, economic, or social harm) than was previously known or recognized.

Any incident that meets all three criteria will be reported study and clinic staff to the Principle Investigator within 48 hours. All serious events related to study participation and death among participants will be reported to the Einstein IRB via:

[contact]

Email: [contact]

Events that require reporting will be graded according to the CTCAE version 5.0. All study related clinic sites have access to this form and it can be downloaded at <http://ctep.cancer.gov>.

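### Patients who refuse photographs enter the primary test with a chart grade that is not blinded by design, and no analysis separates the two grading sources

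*Combined protocol and SAP*

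**What the plan says.** Section 4.4 (Study Procedures) sets up two sources for the radiation dermatitis grade.

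- **Photographed patients:** "Standardized photographs of skin at radiated site to be graded by a dermatologist blinded to study arm". The schedule has photographs at baseline and at the end of radiotherapy.
- **Refusers:** "Should a patient refuse photographs, they may still participate in the study", and the grade in the treating radiation oncologist's "note in the electronic health record will be used in place of clinical photographs". No expected refusal rate and no cap is given.

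The same section adds: "Additional photographs or notes from the chart may be taken in the case of that severe RD develops during treatment". It does not say whether this material contributes to the primary endpoint.

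On who may know the arm, Section 4.4 describes no placebo or sham: "Patients in the control arm will be treated according to standard of care without any RD prophylaxis". Section 4.6 says: "Study key personnel, which includes the treating radiation oncologists, will identify eligible patients". Section 6.4 says: "The treating radiation oncologist will assess for adverse events at each radiotherapy visit as well". Section 5.1 has the statistician randomize and the coordinator hold the key. The dermatologist who reads the photographs is the only person described as blinded.

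Section 5.1 dichotomizes the endpoint as grade 2-5 versus 0-1 and compares the arms as randomized with Pearson's chi-square or Fisher's exact test. A logistic model adjusts for age, gender, BMI, cancer type, radiation dose and concurrent chemotherapy. Grading source appears in neither analysis.

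**The concern.** In a trial without placebo, protection against assessment bias rests on the blinded photograph read. The refusal rule removes that protection for some patients and sends their grades into the same two-by-two table as the blinded ones. The substitute grader sees the patient throughout radiotherapy, asks about adverse events that may include reactions to the wash or ointment, and belongs to the study team.

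The endpoint turns on the step from grade 1 to grade 2. In Figure 1 of the Appendix that step is partly a matter of judgment (faint versus moderate to brisk erythema) and partly a more objective sign (dry versus patchy moist desquamation). If a grader who knows the arm leans one way on borderline cases, the risk difference moves with no true effect behind it. As planned, neither the primary test nor the adjusted model would show that this had happened.

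**Working it through.** **The plan's own figure.** Inputs from Section 5.1: 30 per arm, control incidence 0.38, difference 0.29 (so 0.09 in the intervention arm), two-sided alpha 0.05, power 0.80.

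- Unpooled standard error = sqrt[(0.38×0.62 + 0.09×0.91)/30] = 0.1029.
- Power = Φ(0.29/0.1029 − 1.96) = Φ(0.859) = 0.805.
- Exact power of the uncorrected Pearson test is 0.787.

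The stated 0.80 is reproduced, so the check can use 30 per arm and 0.38.

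**Size of a spurious difference.** Assume no true effect (0.38 in both arms). Let f be the share of patients graded from the chart and s the difference between arms in how often that grader places a patient at grade 2 or above. Then

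spurious difference = f × s.

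Neither f nor s is in the documents, so the values below are assumptions. For each result, the exact rejection probability of the two-sided 0.05 test was obtained by enumerating all 31 × 31 outcomes, with arm rates of 0.38 plus and minus half the difference.

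| Assumed f | Assumed s | Spurious difference | Pearson | Fisher |
|---|---|---|---|---|
| 0 | – | 0 | 0.048 | 0.026 |
| 10% | 20 points | 0.10×0.20 = 0.02 | 0.051 | 0.027 |
| 20% | 30 points | 0.20×0.30 = 0.06 | 0.074 | 0.043 |
| 30% | 30 points | 0.30×0.30 = 0.09 | 0.107 | 0.066 |

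**A second misgrading model.** Suppose the chart grader lowers a share m of true grade 2+ cases in the intervention arm and raises a share u of true grade 0-1 cases in the control arm. Then

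spurious difference = f × (0.38m + 0.62u).

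- f = 10%, m = 50%, u = 0: 0.10×0.19 = 0.019; Pearson 0.050, Fisher 0.027.
- f = 20%, m = 50%, u = 20%: 0.20×(0.19 + 0.124) = 0.063; Pearson 0.076, Fisher 0.045.
- f = 30%, m = 50%, u = 20%: 0.30×0.314 = 0.094; Pearson 0.113, Fisher 0.071.

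The two models agree: little effect at 10%, a visible one at 20-30% with strong bias.

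**Power if only blinded grades are used.** With 30(1 − f) per arm in the unpooled formula above:

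| Refusal | Per arm | Power |
|---|---|---|
| 0 | 30 | 0.805 |
| 5% | 28.5 | 0.785 |
| 10% | 27 | 0.762 |
| 20% | 24 | 0.713 |
| 30% | 21 | 0.655 |

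**The case against.** **Knowledge of the arm.** A reader might infer that the treating oncologists know the allocation. No section says so. The coordinator holds the key, the principal investigator prescribes the agents, and a member of the study team handles the medication calendars. Knowledge of the arm is likely given Sections 4.6 and 6.4, but what the text supports is that the chart grade is not blinded by design. Bias is therefore possible, not established.

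**Severe dermatitis notes.** A reader might also infer that chart notes taken for severe dermatitis are pooled into the endpoint for photographed patients too. Section 4.4 only permits such notes or extra photographs and assigns them no role in grading. Severe cases also lie above the grade 1/2 cut. What remains is an ambiguity. It matters because Section 5.1 counts dermatitis arising at any time in the radiotherapy course, while routine photographs are taken only before and after it.

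**Refusal linked to arm or severity.** This is speculation. The plan does not say when or why patients refuse, and a refusal at the screening photograph would come before any dermatitis.

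**Size.** The magnitude is wholly assumed. Under Fisher's test, which the plan allows, the 20% case stays below 0.05, because that test starts at only 0.026. Even 0.06 is small beside the design difference of 0.29. All of this stands and limits the weight of the point.

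**Intention to treat.** Using a charted grade keeps refusers in the analysis, which is defensible. Setting them to missing and imputing from the same chart grade would not clearly be better. This also stands. It does not explain why no analysis looks at the two sources separately.

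**Conclusion.** The point holds in a limited form. The plan puts a grade that is not blinded by design into the primary endpoint for every refuser and has no analysis that would show its influence. Whether that matters depends on two quantities the documents do not give. At about 10% refusal it is negligible. At 20-30% refusal with a 30-point shift between arms, a spurious difference of 0.06 to 0.09 raises the Pearson error rate from 0.048 to between 0.074 and 0.107, and the Fisher rate from 0.026 to between 0.043 and 0.066. These figures assume no true effect, 0.38 in both arms, 30 evaluable per arm and equal refusal in the two arms. The sample size is unaffected. Because the refusal rate cannot be known in advance, the safeguard should be written before grading begins.

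**What to change.** Keep refusers in the intention-to-treat primary analysis as now planned, and add to Section 5.1:

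1. A repeat of the primary test restricted to patients with a blinded photograph grade.
2. Abstraction of the charted CTCAE grade for all patients at the same end-of-radiotherapy time point, and a repeat of the primary test on that single source. Photographed patients will then have both grades, so any shift between sources can be compared across arms instead of assumed.
3. A table of grading source by arm.

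In Section 4.4, state whether chart notes or extra photographs taken for severe dermatitis during treatment enter the primary endpoint.

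The cost is some chart abstraction and a few lines of analysis-plan text. The blinded-only repeat has less power (0.762 at 10% refusal, 0.655 at 30%) and should be read as a sensitivity analysis. The charted-grade repeat is consistent across patients but not blinded, so neither repeat replaces the primary result. Recruitment and treatment do not change. This is a cheap improvement.

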4.5 Study Calendar and Study Timeline

Study Calendar:

	Screening	Pre-RT (-5 days)	Radiation Therapy Week 2	Radiation Therapy Week 4	Radiation Therapy Week 6 (if applicable)	Radiation Therapy Week 8 (if applicable)	Last day of RT or within 2 weeks of RT completion
Informed Consent	X						
Complete History and Physical	X						X
Randomization	X						
Bacterial Culture Swabs*	X						X
Photographs of skin at radiated site	X						X
Skindex-16 Questionnaire	X						X
Decolonization Regimen		XXXXX	XXXXX	XXXXX	XXXXX	XXXXX	
Patient Medication Calendar**	X	X	X	X	X	X	

* Bacterial cultures obtained via a superficial swab from (1) the nares, (2) skin at the irradiated site and (3) contralateral or other non-radiated skin. This is a non-invasive test using a cotton-tipped applicator inserted into the nostrils or rubbed on the skin,

** A member of the study team will provide the patient with medication calendars prior to the start of each prescribed regimen, and review for compliance throughout treatment. Patients will be asked to initial each date on the supplied calendar when they complete the decolonization protocol in order to assess compliance.

Study Timeline:

	April 2019- April 2020	April 2020 - December 2020
Subject Enrollment	X	
Data Collection	X	X
Statistical Analysis		X
Results Reporting		X

